18.0 Process to Document Consent in Writing

18.1 This study will be following “SOP: Written Documentation of Consent (HRP-091).”

19.0 Data Management

19.1 Data will be managed using the REDCap data management system supported through UH. REDCap is a secure, web-based application for managing online databases. REDCap provides automated export procedures for seamless data downloads to Excel and common statistical packages such as SAS. Case report forms will be produced using built-in features of REDCap.

Feasibility. We will use descriptive statistics to evaluate recruitment and retention rates, attendance at classes, and adherence with online intervention. Retention rate will be reported by group at the end of the study. Attendance will be recorded as the proportion of classes attended for community-based classes; and online video tutorial use, logs of home practice, numbers of logins to the webpage, clicks on education links, downloads and views of videos for the internet-based classes. We will consider study retention successful if the retention rate is at least 80% at 12 weeks, and attendance at in-person classes and home compliance to internet-based lessons is at least 70%. Similar criteria will be set for internet-based compliance as well as home practice compliance in both groups. We will test for non-inferiority of the observed rates relative to the expected rates of retention and attendance assuming that the retention and attendance rates follow a beta-binomial distribution. Non-inferiority margins will be determined as 90% lower confidence bounds on the estimated rate for participants in each group. Maximum likelihood will be used to obtain significance and confidence intervals. Relative risk of non-completion between each Qigong training method and self-care control group will be used to represent study completion rates with inference based on separate Fisher’s exact tests.

Estimating variance for future power calculations. We will use linear mixed models with fixed effects of visit and treatment x post-baseline visit interaction and unstructured covariance among repeated measures to analyze efficacy outcomes. This will yield six variance components required for future power calculations. The Wald statistic from the treatment x visit interaction testing 12-week treatment-dependent response will be used to estimate the effect of Qigong and as a criterion for selecting outcomes that are potentially sensitive to Qigong. Selection of the outcomes to include in our future trial, and which to select as the primary outcome, will also be

FULL PROTOCOL TITLE: CARING FOR CAREGIVERS WITH MIND-BODY EXERCISE

guided by consideration of clinical relevance, participant burden, and cost. The study will have 80% power to identify the outcome that is truly most responsive to Qigong from among the 14 measures calculated from the 12 assessments completed at 12 weeks if the most responsive measure is associated with an effect size at least 0.43 SD greater than the others.

Inter-rater reliability and validity testing of proficiency instrument. Inter-rater reliability will be evaluated using Cohen's Kappa statistic. Validity testing based on cross-sectional comparisons of proficiency scores and practitioner's years of training will utilize Pearson's correlations. Associations between longitudinal changes in proficiency and clinical outcomes will be evaluated using mixed model approaches described above.

Qualitative analysis. Semi-structured qualitative interviews will be audio recorded and transcribed verbatim. Thematic analysis will be informed by grounded theory methods to guide description of qualitative interviews. Questions will focus on facilitators/barriers to recruitment/participation, and acceptability of the intervention and its specific components. Two investigators will independently code transcripts to identify emergent themes in an iterative process until thematic saturation is reached as in prior studies.^{47, 48 49-51} Transcription, coding, and analysis will be conducted in NVivo v11.

- 19.2 Three documents will have identifiable data: Informed Consent (name), Screening Questionnaire (name, age, ethnicity, phone number, and email address), and Screening Log (name, phone number). At the baseline assessment, each participant will be given a unique study ID that does not contain personal identifying information and will be used for all research purposes. All physical study data will remain locked at all times in a file cabinet in the PI's office, and all electronic study data will be password protected with access restricted to approved personnel. Study reports will be aggregated so that individual participants are not identified. All data will be stored in databases, identified only by study ID number, behind appropriate firewalls and with institutional backup.
- 19.3 All data sets will be verified for accuracy by the PI, Co-PI, and grant coordinator. Research data and subject files will be audited for accuracy during the initial months of testing/interviewing and subsequently every 6 months. All REDCap data and subject files will be double cross-checked after they have been entered and/or stored.
- 19.4 Identifiable data will be stored in a locked file cabinet in [name] office. Names, code numbers and telephone numbers will be kept in locked secure files, separate from the study data. Any document linking the participant name to an identification number will be kept in a locked file separate from data collection files.
- 19.5 Data will be stored for up to 5 years from the completion of the study date (08/31/2026) or by the time all data has been published in manuscript format, whichever comes first.

FULL PROTOCOL TITLE: CARING FOR CAREGIVERS WITH MIND-BODY EXERCISE

19.6 Only the research team will have access to the data.

19.7 The research team will be responsible for the receipt of data.

19.8 Not applicable.

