1.0 Objectives

1.1 Using cancer caregivers (CCGs) as a representative population of the larger CG population, our long-term goal is to conduct a large-scale fully powered trial evaluating a widely accessible and previously studied Qigong regimen (Eight Brocades, *Baduanjin Qigong*). The goal of this R34 is to conduct a mixed-methods pilot randomized controlled trial (RCT) to inform the feasibility and design of a future larger definitive trial.

Primary Objectives:

1. To finalize intervention content and delivery of both in-person community-based group and individual internet-based Qigong protocols.
2. To assess the 'learnability' of Qigong delivered in community-based group classes and via an internet-based protocol using a novel proficiency instrument.
3. To evaluate the feasibility of recruiting and retaining cancer caregivers into a 12-week clinical trial, and completing all outcomes testing protocols.

1.2 We hypothesize that participant recruitment, retention, and adherence to intervention and assessment protocols will comply with target goals. Feasibility will be assessed with respect to participant recruitment, retention, intervention adherence, and intervention acceptability. We will assess recruitment feasibility by the number of screened and eligible participants and the number refusing to participate. We will document reasons for refusal. This domain of feasibility will require: a) $\geq 50\%$ screened individuals are study eligible and b) $\geq 5-10\%$ of eligible participants are willing to consent. With a goal of $n = 54$ enrolled over a one-year period, we will need to screen 14 participants per month. Participant retention will be deemed feasible if loss to follow-up is $\leq 20\%$. Intervention adherence will require: a) $\geq 70\%$ participation in community or internet-guided classes and $> 50\%$ compliance with home practice guidelines. Qualitative interviews with CCGs, including those who drop out and have low adherence, will be used to further inform overall study feasibility, and facilitators and barriers to participation.

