5.0 Number of Subjects

LOCAL:

5.1 We expect to consent, enroll, and randomize a total of 54 CCGs.

5.2 The sample size was based on practical/budgetary constraints as well as a preliminary power analysis. A power analysis was conducted to determine the minimum sample

FULL PROTOCOL TITLE: CARING FOR CAREGIVERS WITH MIND-BODY EXERCISE

size that is required to find significance with a power set of .80, an alpha level at .05, correlation among the repeated measures of 0.3, and a moderate effect size of .25 using G*Power version 3.1. Based on the primary analysis, to ensure sufficient power on the repeated measure ANOVA (3 time points x 3 groups), a total of 48 participants are required. In consideration of 10-15% of attrition rate, a total of 54 participants will be recruited.

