7.0 Study Timelines

7.1 For Cohorts 1 and 2, we will randomize (1:1:1) 24 CCGs to one of three conditions: (1) A community- based Qigong program; (2) an internet-based Qigong program; or (3) a self-care control group. For Cohort 3, we will randomize (2:1) 15 CCGs to one of two conditions: (1) an internet-based Qigong Program, or (2) a self-care control group. For Cohort 4, we will randomize (2:1) 15 CCGs to one of two conditions: (1) a community-based Qigong program, or (2) a self-care control group. Our primary outcomes are feasibility and acceptability.

7.2 Participants in the community-based programs will attend one, 75 minutes class per week supplemented by home practice (guided by printed materials) for 20 minutes on 3 additional days. Participants in the internet-guided program will be asked to follow two online sessions for 40 minutes each, also supplemented by home practice for 20 minutes on 3 additional days. Participants in both Qigong groups will commence training within 2 weeks of baseline visits. Caregivers randomized to either Qigong intervention can expect a total time commitment of 30 hours to complete all study related activities.

Individuals randomized to the self-care control group will be provided with an educational book on caregiving, they will also be provided with a “Self-Care Manual” that includes self-guided activities related to caregiving and caregiver health. Caregivers randomized to this group can expect about a 5-hour total time commitment to study related activities.

7.3 Baseline and 12-week assessments including psychosocial measures and QOL, physical function and cognitive measures will occur in person for all participants at the University of Houston College of Nursing in Sugarland, [name]. In addition, a short qualitative interview will be conducted with participants in the community-based and internet-based classes. A longer-term 6-month follow-up will assess psychosocial and QOL measures using a mail-in questionnaire packet. Primary analyses should be complete by 08/31/2021.

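### Section 19.1 fits a beta-binomial to 12-week retention, which is one yes/no per participant; the model reduces to a plain binomial, and the large-sample bound left for 18 people per arm should be replaced by an exact one

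*Combined protocol and SAP*

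**What the plan says.** All references are to the combined protocol and SAP.

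- **Success rule (section 19.1, Feasibility).** "We will consider study retention successful if the retention rate is at least 80% at 12 weeks". Section 1.2 puts the same rule as a loss: "Participant retention will be deemed feasible if loss to follow-up is" at most 20%.
- **Model (19.1).** The observed rates are compared with the expected ones "assuming that the retention and attendance rates follow a beta-binomial distribution". One model therefore serves both kinds of rate.
- **Inference (19.1).** "Maximum likelihood will be used to obtain significance and confidence intervals". And: "Non-inferiority margins will be determined as 90% lower confidence bounds on the estimated rate for participants in each group". The text does not say whether the interval is Wald, profile likelihood or another form. Nor does it say whether 90% means a 10% tail or the lower limit of a two-sided interval (5% tail).
- **Data type (19.1).** "Attendance will be recorded as the proportion of classes attended for community-based classes".
- **Size.** Section 5.1: "We expect to consent, enroll, and randomize a total of 54 CCGs". Section 7.1: "For Cohorts 1 and 2, we will randomize (1:1:1) 24 CCGs to one of three conditions". Cohorts 3 and 4 each randomize 15 at 2:1.

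**The concern.** A beta-binomial describes counts out of several trials per unit, with extra variation between units. Class attendance has that form: one community class a week for 12 weeks gives up to 12 trials per person. Retention does not, since a participant is either retained at 12 weeks or lost. The second parameter of the model then has nothing to be estimated from, and a two-parameter fit has a flat direction.

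Once the redundant parameter is set aside, the plan rests on a likelihood-based lower bound for a proportion near 1 in about 18 people. Large-sample bounds are weakest there and tend to sit too high. Retention is part of a primary objective (section 1.1) and is meant to inform a larger trial, so an over-favourable bound would make an arm's retention look more secure than the data show.

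**Working it through.** **Inputs.** Cohorts 1 and 2: 24 at 1:1:1, so 8 per arm (24 is read as the total for both cohorts, since 24 + 15 + 15 = 54, the planned total). Cohort 3: 10 internet, 5 control. Cohort 4: 10 community, 5 control. Arm totals: community 8 + 10 = 18, internet 8 + 10 = 18, control 8 + 5 + 5 = 18. Target 0.80. Planned attrition 10–15% (section 5.2), so expected retention is 0.85–0.90. The plan states no bound, power or sample size for the retention test, so there is no figure of its own to reproduce.

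**Step 1: is the over-dispersion parameter identified?** With one trial per unit and mean μ = α/(α+β), P(Y = 1) = μ whatever the intraclass correlation ρ = 1/(α+β+1). The log-likelihood is x·ln μ + (n−x)·ln(1−μ), which does not contain ρ. For 15 of 18 retained it is 15·ln(15/18) + 3·ln(3/18) = −8.110. Direct evaluation gave this same value at ρ = 0.01, 0.1, 0.3, 0.6 and 0.9. The mean is still estimated, at 15/18 = 0.833. On simulated 12-class attendance data for 18 people, the log-likelihood does change with ρ (from −106.1 to −141.8 over the values tried), so the model can be fitted there.

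**Step 2: lower bounds at n = 18.** With p̂ = x/n and tail t:

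- Wald: p̂ − z·√(p̂(1−p̂)/n), with z = 1.2816 for t = 0.10.
- Profile likelihood: the p below p̂ at which 2[ℓ(p̂) − ℓ(p)] = z². At 18/18 this is exp(−z²/36) = 0.955.
- Exact (Clopper-Pearson): the t quantile of Beta(x, n−x+1). At 18/18 this is 0.10^(1/18) = 0.880.

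| Retained | Wald | Profile | Exact |
|---|---|---|---|
| 15/18 | 72.1% | 70.3% | 66.6% |
| 16/18 | 79.4% | 77.2% | 73.1% |
| 17/18 | 87.5% | 84.8% | 80.1% |
| 18/18 | 100% | 95.5% | 88.0% |

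**Step 3: coverage of the nominal 90% bound**, summing binomial probabilities over outcomes whose bound does not exceed the true rate:

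| True retention | Wald | Profile | Exact |
|---|---|---|---|
| 0.75 | 86% | 86% | 96% |
| 0.80 | 90% | 90% | 90% |
| 0.85 | 78% | 95% | 95% |
| 0.90 | 85% | 85% | 100% |
| 0.95 | 60% | 60% | 100% |

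For example, at 0.90 the Wald and profile bounds miss only when all 18 are retained, which has probability 0.9^18 = 0.150; coverage is 0.850.

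**Step 4: decision against 80%.** This reads the lower bound against the target.

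- 10% tail: all three bounds first reach 0.80 at 17/18. Type I error at 0.80 is 18·0.8^17·0.2 + 0.8^18 = 0.0811 + 0.0180 = 0.099.
- 5% tail: at 17/18 the bounds are Wald 0.856, profile 0.812, exact 0.762. Wald and profile pass, with type I error 0.099 against a nominal 0.05. Exact passes only at 18/18 (0.847), with error 0.8^18 = 0.018.

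**The case against.** The strongest reply is that little turns on this, and much of that reply stands.

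- A reader might infer that the retention analysis cannot be run or will fail to converge. The documents do not support that. Only the over-dispersion parameter is lost; the rate is estimable as a plain binomial.
- A reader might take the Wald figures, including the 100% bound at 18/18, as the plan's own. The plan does not name Wald. Profile likelihood is equally a maximum-likelihood method and does better at 0.85 (95% against 78%). It still under-covers at 0.75, 0.90 and 0.95, so the small-sample concern is not confined to Wald. A Wald bound on the logit scale behaves differently again: it has no value at 18/18, and with a 5% tail it falls just below exact at 17/18 (0.758 against 0.762).
- A reader might infer that arms will be passed wrongly. With a 10% tail they are not, because the pass mark and error rate are the same for Wald, profile and exact. Under-coverage at 0.85 and above arises where the target is truly met.
- Section 19.1 also states success as an observed rate and uses descriptive statistics by group. That rule does not call on the beta-binomial.
- Cohort could serve as the cluster for retention, but the plan does not say so, and each Qigong arm would have only three cohorts.
- Clopper-Pearson is conservative, and other small-sample limits can be defended.

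What the reply does not remove is that the stated model is the wrong one for this outcome, and that interval type and tail are left open in a way that can move the pass mark.

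**Conclusion.** The point holds as a mis-specified model and an under-specified bound. For retention the beta-binomial adds a parameter about which the data say nothing. The likelihood bound that remains exceeds the exact one at n = 18 by about 4 to 12 percentage points in the 10%-tail table (profile 3.7 points at 15/18; Wald 12.0 at 18/18). Its coverage is 85% at true retention 0.90 for both Wald and profile, while the exact bound is not below 90% at any rate examined.

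The effect on decisions is conditional: none per arm with a 10% tail, and a shift from 17/18 to 18/18 if the bound is the lower limit of a two-sided 90% interval. The observed-rate rule and the attendance analysis are untouched.

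This rests on 18 per arm as allocated, one retention status per participant, independence between participants, and the lower bound being read against 80%. Whether the non-inferiority margin itself is properly defined is a separate question.

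**What to change.** In section 19.1, restrict the beta-binomial to class or lesson attendance, counted out of a fixed number per person. For retention, add a sentence such as: *Retention at 12 weeks will be analysed as a binomial proportion and reported for each arm with an exact (Clopper-Pearson) lower confidence limit, read against the 80% target; the limit is [one-sided 90% / the lower limit of a two-sided 90% interval].* The sponsor should choose the tail and state it before the data are seen. The same paragraph already uses Fisher's exact test for non-completion, so exact inference for this outcome fits the existing plan.

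The cost is wording only, with no new data or design change. The downside is that exact limits are conservative, so the reported retention bounds become somewhat less favourable (at 17/18, 80.1% in place of 84.8% or 87.5%), and with a 5% tail an arm would have to retain all 18 for its limit to clear 80%.

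### The added non-inferiority test of retention and attendance (section 19.1) takes its margin from each group's own 90% lower confidence bound, so it has no fixed margin and no stated pass rule

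*Combined protocol and SAP*

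**What the plan says.** The feasibility paragraph of section 19.1 has two layers.

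The first is descriptive, with fixed targets. It opens "We will use descriptive statistics to evaluate recruitment and retention rates" and then sets the criterion: "We will consider study retention successful if the retention rate is at least 80% at 12 weeks". Attendance at in-person classes and compliance with internet lessons must be at least 70%. Section 1.2 agrees: "Participant retention will be deemed feasible if loss to follow-up is" no more than 20%, and adherence requires at least 70% "participation in community or internet-guided classes".

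The second is a formal test, under a beta-binomial model: "We will test for non-inferiority of the observed rates relative to the expected rates of retention and attendance". Its margin is defined in one sentence: "Non-inferiority margins will be determined as 90% lower confidence bounds on the estimated rate for participants in each group". The next sentence names maximum likelihood as the source of significance and confidence intervals.

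Neither section 19.1 nor any other section gives a number for the margin, a significance level for this test, or the comparison that counts as a pass. The expected rates have no value in the test sentence; 80% and 70% are the natural reading. The paragraph does not say how the test result relates to the fixed targets.

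**The concern.** A non-inferiority margin is the shortfall one is prepared to accept, and it has to be set before the data can speak to it. Here it is a function of the estimate being tested. It differs between groups, changes with the observed rate and grows as precision falls.

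The sentence also does not lead to one rule. At least three can be read from it:

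- **Shortfall reading:** the observed rate may fall below the expected rate by up to the distance between estimate and lower bound.
- **Bound reading:** the lower bound itself must reach the expected rate.
- **Literal reading:** the observed rate is compared with its own lower bound. This always passes and tests nothing.

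Section 7.1 names feasibility and acceptability as the primary outcomes, and the pilot exists to inform a definitive trial. A formal non-inferiority statement on retention or attendance would be read in that light, and two competent analysts could reach opposite statements from the same data.

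**Working it through.** **No figure of the plan to reproduce.** The test has no stated sample size, level or power. The sample size in section 5.2 (48, raised to 54) is for a repeated-measures ANOVA. It does reproduce as a group-by-time interaction (power 0.81 at N = 48), but it has no bearing on this test.

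**Inputs.**
- Arm size, section 7.1: "For Cohorts 1 and 2, we will randomize (1:1:1) 24 CCGs to one of three conditions", then 15 in cohort 3 and 15 in cohort 4, each 2:1. Reading 24 as the total for cohorts 1 and 2 gives 24 + 15 + 15 = 54, which matches section 5.1. Per arm: community 8 + 10 = 18; internet 8 + 10 = 18; control 8 + 5 + 5 = 18.
- Expected retention p0 = 0.80 (my reading of the expected rate).
- Bound L: one-sided 90% lower bound. Retention is one yes/no result per participant, so the beta-binomial reduces to the binomial.

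**Rules**, with estimate p = x/18 and distance d = p − L:
- Shortfall reading: pass if p ≥ p0 − d, that is, p + d ≥ 0.80.
- Bound reading: pass if L ≥ 0.80.
- Fixed 80% figure applied to one arm: 0.80 × 18 = 14.4, so 15/18. The plan words its target for study retention; applying it to one arm is for comparison only.

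**Bounds at the deciding counts (exact, Clopper-Pearson).**

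| x/18 | p | L | d | p + d | Shortfall | Bound |
|---|---|---|---|---|---|---|
| 11 | 0.611 | 0.433 | 0.178 | 0.789 | fail | fail |
| 12 | 0.667 | 0.488 | 0.179 | 0.845 | pass | fail |
| 13 | 0.722 | 0.545 | 0.177 | 0.900 | pass | fail |
| 16 | 0.889 | 0.731 | 0.158 | 1.047 | pass | fail |
| 17 | 0.944 | 0.8005 | 0.144 | 1.088 | pass | pass |

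The plan names maximum likelihood, so I repeated the check with likelihood-ratio bounds. Shortfall reading: p + d is 0.762 at 11/18 and 0.816 at 12/18. Bound reading: L is 0.772 at 16/18 and 0.848 at 17/18. The thresholds of 12 and 17 are unchanged. The size of the margin does depend on the method: at 13/18, d is about 14.6 points by likelihood ratio and 17.7 by the exact bound.

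**Pass probabilities**, P(X ≥ threshold) with X binomial(18, true rate):

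| True retention | Shortfall (≥12) | Fixed 80% figure (≥15) | Bound (≥17) |
|---|---|---|---|
| 70% | 72% | 16.5% | 1.4% |
| 80% | 95% | 50% | 9.9% |
| 90% | 99.9% | 90% | 45% |

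On the shortfall reading, 12/18 is also the lowest count whose upper one-sided 90% exact bound reaches 80%. In effect that reading declares non-inferiority whenever the data fail to show a shortfall, which is why imprecision helps.

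**Attendance, illustration under an assumption.** The community arm has 18 participants and one class a week for 12 weeks (sections 7.2 and 9.2), so 216 attendances; p0 = 0.70. The documents give no within-person correlation ρ, so I show a range. With SE = √[p(1 − p)(1 + 11ρ)/216] and d = 1.2816 × SE, the lowest mean attendance that passes on the shortfall reading solves p + d = 0.70. It is 63.9% at ρ = 0.1, 61.2% at ρ = 0.3 and 59.1% at ρ = 0.5. The more uneven attendance is between participants, the lower the bar.

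**The case against.** **No decision depends on the test.** This stands. The fixed targets in sections 1.2 and 19.1 define success, and nothing lets a pass on the added test overturn a missed target. A reader might infer that the plan has no valid feasibility threshold, or that its feasibility decision is compromised. The documents do not support that.

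**The authors probably meant that the bound must reach 80% or 70%.** Possible, and that reading does not reward imprecision. But the text calls the bound the margin, not the criterion. On that reading an arm with true retention of 90% would fail more often than not (45% pass), which the plan should state if it is intended.

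**A valid non-inferiority test can also pass a rate below 80%.** True. Passing at 67% is not a fault in itself; the fault is that the permitted shortfall comes from the data.

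**A 90% lower bound is ordinarily one-sided.** Accepted, and used above. If the lower limit of a two-sided 90% interval were meant, the exact thresholds would be 11/18 and 18/18, so the point merits a word of clarification but no more.

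Two further inferences go too far. One is that the reading will be picked once results are known: nothing in the documents says so, only that it could be. The other is to apply the rule to all 54 participants pooled and set the result against the study-level 80% target: section 19.1 sets the margin group by group, so that is not the test described.

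**Conclusion.** The point holds for the added test only. Its margin is derived from the rate under test, and no numeric margin or pass rule is given. This is more than missing detail: the stated rule cannot work as a margin and, on the shortfall reading, becomes more lenient as information falls. With 18 per arm the count needed for retention is 12 or 17 depending on the reading, against 15 for the fixed figure applied to one arm, so neither reading agrees with the plan's own 80%.

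The retention figures rest on three assumptions: 18 participants analysed per arm, 80% as the expected rate, and one-sided 90% bounds. The thresholds are the same for exact and likelihood-ratio bounds. The attendance figures also rest on an assumed correlation and are illustrative. It should be fixed, but it does not undermine the feasibility criteria.

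**What to change.** Either of two changes to section 19.1 is enough.

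1. Keep the test and define it. Replace the data-derived margin with a numeric margin, or a minimum acceptable rate, fixed in advance for each outcome. State the reference rate, the confidence level (and that the bound is one-sided, if so), the pass rule, and that the test supports the fixed targets and does not replace them. To show what this involves, with a floor of 65% (an arbitrary figure, not from the documents) a one-sided 90% exact bound above the floor needs 15/18. The chance of passing is then 7.8% at true retention of 65% and 72% at 85%.
2. Drop the test and the margin sentence. Report each group's rate with a confidence interval (exact binomial for retention, beta-binomial for repeated attendance or session data) against the existing 80% and 70% targets.

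The cost is wording only: no extra participants, visits or data. The downside is that the formal non-inferiority statement becomes stricter under the first option than on the shortfall reading, and is lost under the second.

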9.3 The Qigong Instrument used is the Eight Brocade Protocol. Qigong is an increasingly popular multi-modal mind-body exercise that shows promise in addressing a broad range of psychosocial and physical factors highly relevant to CGs. Sharing many characteristics with Tai Chi, Qigong incorporates elements of slow gentle movement, breath training, and a number of cognitive skills including heightened body awareness, focused mental attention, and imagery—which collectively may afford greater benefits to health compared to unimodal therapies.²⁸⁻³⁰

Week	Activities	Approx. Duration (in minutes)
1-2	Check-in	2
	Qigong Warm-up Exercises	
	Qigong Swinging and Drumming the Body	
	Swinging Up and Down	
	Spiraling the Waist	
	Mindful stretching	
	Lower Extremities (feet, ankles, knees)	20
	Upper Extremities (hands, arms, shoulders)	
	Spinal Cord Breathing	
	Washing with Qi from the Heaven	
Tan Tien Breathing		
Introduction to Eight Brocades Movements #1-4	35	
#1 Holding the Hands High to Regulate Internal Organs		
#2 Posing as an Archer Shooting Both Left- and Right-Handed		
#3 Holding One Arm Aloft to Regulate Spleen and Stomach		
#4 Looking Backwards to Prevent Sickness and Strain		
Cool-Down Exercises	3	
Self-massage and meridian tapping		
3-8	Check-in	2
	Qigong Warm-up Exercises	10
	Review/ Practice Eight Brocades Movements #1-4	15
	Learn and practice Eight Brocades Movements #5-8	30
	#1 Swinging the Head and Lowering the Body to Relieve Stress	
	#2 Moving Hands Down Back and Legs, and Touching Feet to Strengthen Kidneys	
	#3 Thrusting Fists and Making Eyes Glare to Enhance Strength	
	#4 Raising and Lowering the Heels to Cure Diseases	
Cool-Down Exercises	3	
9-12	Check-in	2
	Qigong Warm-up Exercises	10
	Review/ Practice/ Refine Eight Brocades Movements #1-8	45
	Cool-Down Exercises	3

9.4 In addition to caregiver distress, medical history and demographics, the following outcomes will be assessed at baseline, 12-weeks, and 6-months:

The following will be measured at baseline and 12-weeks:

FULL PROTOCOL TITLE: CARING FOR CAREGIVERS WITH MIND-BODY EXERCISE

- Grip strength of the dominant hand will be measured using a **Jamar hydraulic hand dynamometer** (Patterson Medical – Canada, Mississauga, ON, CAN).⁴⁴

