10.0 Setting

10.1 The baseline assessment and 12-week follow-up assessment components of the research will take place at the University of Houston College of Nursing Campus at [name]. The Community-based Intervention group Qigong classes will take place at [name]. Classes will be held every Wednesday at 2pm.

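### Section 19.1 makes no allowance for group classes in the community arm, so if outcomes correlate within class its standard errors and the future sample size would be too small

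*Combined protocol and SAP*

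**What the plan says.** The paragraph of section 19.1 on estimating variance specifies linear mixed models with fixed effects for visit and for treatment by post-baseline visit, and "unstructured covariance among repeated measures to analyze efficacy outcomes". It continues: "This will yield six variance components required for future power calculations". "The Wald statistic from the treatment x visit interaction testing 12-week treatment-dependent response" is then used to estimate the effect of Qigong and to help choose outcomes for the definitive trial.

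On delivery, sections 7.2 and 9.1 have the community arm taught in instructor-led groups, one class a week, and section 10.1 gives a single slot: "Classes will be held every Wednesday at 2pm". The internet arm works individually. Section 12.2 describes the eventual large trial as also using community group classes.

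On visits, section 7.3 states: "A longer-term 6-month follow-up will assess psychosocial and QOL measures using a mail-in questionnaire packet". Section 9.4 likewise says that "the following outcomes will be assessed at baseline, 12-weeks, and 6-months", but introduces grip strength, Timed Up-and-Go, Digit Span and Trail Making with "The following will be measured at baseline and 12-weeks".

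No class, instructor or cohort term, ICC or design effect appears anywhere in the analysis plan.

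**The concern.** People who share an instructor, a room and a group for 12 weeks may end up more alike than people who do not. Section 12.2 itself presents group support as a reason for choosing the classes, so a positive within-class correlation is plausible, though nothing in the documents establishes one. A model with covariance only within participants treats classmates as independent.

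Two things would follow from a positive correlation. In the pilot, the SE of the community v control contrast at 12 weeks would be too small and its Wald statistic too large. In the definitive trial, a community-arm size computed from the visit-level components alone would fall short of its nominal power. The second matters more, because supplying variances for that calculation is the stated purpose of the paragraph, and the plan describes the visit-level components as the ones required.

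**Working it through.** **The plan's own figure.** An unstructured covariance matrix over t visits has t(t+1)/2 parameters. For t = 3 this is 3×4/2 = 6 (three variances, three covariances), which reproduces the stated six. For t = 2 it is 2×3/2 = 3. Three is complete for a baseline and 12-week comparison, so the count affects no estimate or test.

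**Arm sizes (section 7.1).** Cohorts 1 and 2 together: 24 at 1:1:1, so 8 per arm. Cohort 3: 10 internet, 5 control. Cohort 4: 10 community, 5 control. Community: 8 + 10 = 18. Control: 8 + 5 + 5 = 18. The cohorts sum to 24 + 15 + 15 = 54, as in section 5.1.

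**Assumptions not in the documents.** Cohorts 1 and 2 are equal in size, and each cohort with a community arm forms one class, giving classes of 4, 4 and 10. The ICC for the 12-week response lies between 0.01 and 0.10. The two arms have equal outcome variance. Dropout is ignored.

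**Pilot.** Effective class size = Σm²/Σm = (16 + 16 + 100)/18 = 7.33. Design effect DE = 1 + (7.33 − 1)×ICC. With 18 per arm and clustering in one arm only, true SE / model SE = √((DE + 1)/2). The shortfall in the model SE is 1 − 1/ratio. The actual level of a nominal 5% test uses a normal approximation.

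| ICC | DE | True SE / model SE | Model SE too small by | Actual level of nominal 5% test |
|---|---|---|---|---|
| 0 | 1.00 | 1.00 | 0 | 5.0% |
| 0.01 | 1.06 | 1.02 | about 1.5% | 5.4% |
| 0.05 | 1.32 | 1.08 | about 7% | 6.9% |
| 0.10 | 1.63 | 1.15 | about 13% | 8.8% |

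If Cohorts 1 and 2 were instead taught as one class (classes of 8 and 10), effective class size is (64 + 100)/18 = 9.11, and the SE ratios become 1.02, 1.10 and 1.19 at ICC 0.01, 0.05 and 0.10.

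**Definitive trial.** Assume classes of 10, so the community-arm multiplier is 1 + 9×ICC. The two-arm total rises by (multiplier + 1)/2. As an illustration, assume a standardised difference of 0.5, for which independence gives 63 per arm at 80% power.

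| ICC | Community-arm multiplier | Two-arm total multiplier | True power with 63 per arm | Needed per arm, equal arms |
|---|---|---|---|---|
| 0.01 | 1.09 | 1.045 | 78% | 66 |
| 0.05 | 1.45 | 1.225 | 72% | 77 |
| 0.10 | 1.90 | 1.45 | 64% | 92 |

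**Could the pilot estimate class variance?** Three classes leave 2 degrees of freedom. The 95% limits for a variance are then 2/χ²(0.975) to 2/χ²(0.025), or about 0.27 to 39 times the estimate. With one class per cohort, class also cannot be separated from cohort within the community arm.

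**The case against.** The plan can fairly be defended on several counts.

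- A reader might infer that six is a miscount and that it makes future power look better than it is. The documents do not support that. Six is right for the three-visit questionnaires and fits the three time points in section 5.2. Fitting the stated model to two-visit data returns three parameters in any case, and the Wald test is at 12 weeks. The sentence is over-general and has no effect on results.
- A reader might infer that the SEs are too small as a matter of fact. The documents give no ICC, class sizes or number of classes. At ICC 0 there is no error, and at 0.01 it is about 2% on the SE of the difference. The conclusion is conditional.
- A reader might infer that a class random effect should have been fitted. With about three classes it could not be estimated usefully, so leaving it out of the pilot model is understandable.
- The primary outcomes are feasibility and acceptability (section 7.1), and the efficacy model supports no confirmatory claim. If the ICC were the same for every outcome, every community v control Wald statistic would shrink by the same factor, leaving their order unchanged. Clinical relevance, burden and cost also guide the choice of outcomes.
- The plan calls the components required, not sufficient, and nothing prevents a design effect from being added later.

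All of this stands as a limit on size and importance. It does not remove the gap. The paragraph exists to specify what the future power calculation needs, that trial would again use group classes, and the plan mentions neither the missing component nor a substitute for it.

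**Conclusion.** The point holds as a minor, conditional one. Section 19.1 treats community-arm participants as independent although they are taught in groups, and offers the visit-level components as those needed for planning. If the within-class correlation is positive, community-arm SEs here and the future community-arm size would be too small. Over the assumed ICC range the SE understatement in the pilot runs from slight to moderate. The effect on the definitive trial could be larger: at ICC 0.10 with classes of 10, the community arm would need nearly twice its size under independence. These sizes rest on assumed ICCs and class sizes and show a range; they do not estimate the error. The internet arm is taught individually and is not affected by class clustering. No primary conclusion of the pilot changes. The component count is a separate matter of wording and contributes nothing to the optimism.

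**What to change.** In section 19.1:

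1. State that class-level variance cannot be reliably estimated from the few community classes in this pilot, and record each community participant's class.
2. Report the 12-week community v control SEs and Wald statistics as planned and also, as a sensitivity analysis, inflated for ICCs from 0.01 to 0.10 using the actual class sizes.
3. State that the future power calculation will multiply the community-arm size by 1 + (m − 1)×ICC over the same range, where m is the planned class size.
4. As a wording correction only, say that the model yields six components for three-visit measures and three for two-visit measures.

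The cost is a few sentences and one extra data field. The sensitivity SEs, and any intervals built on them, will be somewhat wider, and the planned community arm will be larger. The main model and the pilot's sample size stay as they are.
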